At Weeks 0, 12, and 48, applicable subjects will complete the Body Image Scale (mBIS) questionnaire, and answer questions about general hormone therapy satisfaction.

SUB-STUDY STATISTICAL CONSIDERATIONS

Sample Size and Power

The primary aim of this analysis is to determine if PrEP interacts with hormone therapy in either direction that would impact either i) efficacy of PrEP to reduce HIV acquisition or ii) hormones to achieve desirable gender traits. Of our 300 person cohort, we estimate that 280 individuals will be MAAB Of those 280 MAAB, we predict that 70% will be taking feminizing hormones (n=196) and 30% will be on no hormonal therapy (n=84), based on previous population estimates (97). Based on adherence results in individuals randomized to iTAB (98), we estimate that 25% of participants will have perfect adherence to PrEP.

[figure not shown]

Figure 2: Predicted Numbers of Individuals on HRT and PrEP

Statistical power is based on a one-sample non-inferiority test to see if the TFV-DP concentration of perfectly adhered MAAB persons is equivalent to MSMs on average under an acceptable margin. The following assumptions are made: i) Using PK modeling of HIV-uninfected men and women, it has been shown that perfect adherers (i.e. daily dosing for 7 days) have TFV-DP concentrations of 1560 (IQR 1246-2029) fmol/punch as determined in MSM; ii) Since this is a non-inferiority study, we will assume the expected sample mean for MAAB is around 1560 fmol/punch, or slightly lower. In other words, we will assume the mean difference in TFV-DP concentrations between MAAB and MSMs is approximately 0 (ranges from -180 to 50); and iii) We believe that a difference of less than 230 fmol/punch (equivalent to 1 tablet per week dosing) in the TFV-DP concentration can be considered non-inferiority which will be the lower limit of acceptable variation. Thus, we will set the non-inferiority margin to be 230.

Assuming the standard deviation is 350, if the true mean TFV-DP concentration for MAAB is 1360 fmol/punch (ie, 100 fmol/punch lower than MSMs), then 45 subjects are required to be 80% confident that the lower limit of a one-sided 95% confidence interval of the mean difference between MAAB and MSMs will be above the non-inferiority limit of -230.

Analysis Plan

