Vaginal swab for herpesvirus and HPV			X			
Vaginal swab for vaginitis multicomplex			X			

Sub-study IV Statistical Considerations

Aim 1: To determine the impact of pro-inflammatory STIs on CVF TFV levels.

We will quantify CVF TFV levels of participants at week 24 and compare levels in those with and without the presence of active vaginal infections using methods for continuous measures (i.e., the Student t test or Wilcoxon test depending on distributions). The primary analysis will compare those with any infection to those with no detected infection. We will examine individual organisms in subanalysis. We will also compare the proportion of participants with TFV levels in steady state (\geq 50 ng/mL) to those with levels that are not (<50 ng/mL) at week 24 for vaginal infections using Fisher's exact test. The threshold of \geq 50 ng/mL was selected based on previously reported CVF steady state trough concentrations at 24 hours achieved by oral dosing (\leq 11).

Sample Size: Based on an estimated mean concentration of 119 ng/mL and a standard deviation of 58 ng/mL in CVF TFV in a steady state PK study(32), we have 80% power with a one-sided lower bound alpha of 0.05 to detect a difference in individuals with STIs versus those without STIs of 33 ng/mL or 28% reduction in CVF TFV levels in a sample of n=40.

Aim 2: To determine the impact of CV inflammation on CVF TFV levels.

We will compare TFV levels as a continuous measure with \log_{10} -transformed cytokine levels at week 24 using the Pearson correlation test or Spearman correlation test if they are not normally distributed. For assessment of chronic inflammation and TFV levels, we will compare those with and without elevated cytokine levels of at least one cytokine (MIP-1 α and β , IP-10, IL-6 and IL-8) that remains higher at both baseline and week 24 using Student t-test or Wilcoxon depending on distributions. If cytokine levels are below the level of detection in \geq 40% of samples, these will be converted to categorical variables (detectable versus undetectable).

Exploratory Aim: To assess the impact of the CV microbiome on CVF TFV levels.

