integrase inhibitors, protease inhibitors or investigational antiretroviral agents) – if currently on TDF/FTC for PEP or PrEP they can switch to study provided drug but can not continue any other antiretroviral agent.

- Agents with known nephrotoxic potential:
 - aminoglycoside antibiotics (including gentamicin)
 - IV amphotericin B
 - cidofovir
 - o cisplatin
 - foscarnet
 - IV pentamidine
 - IV vancomycin
 - o oral or IV gancyclovir
 - other agents with significant nephrotoxic potential
- Drugs that slow renal excretion
 - Probenecid
- Immune system modulators
 - Systemic chemotherapeutic agents (i.e. cancer treatment medications)
 - Ongoing systemic corticosteroids (with the exception of short courses of tapering steroid doses for asthma or other self- limited condition).
 - Interleukin-2 (IL-2)
 - Interferon (alpha, beta, or gamma)
- Other agent known to have a significant interaction with TDF or FTC
- 6. Proteinuria 2+ or greater by urine dipstick
- 7. Pregnancy (if individual has a uterus)
- 8. Other condition that in the opinion of the investigator would put the participant at risk or interfere with participation, complicate interpretation of study outcome data, or otherwise interfere with achieving the study objectives.

Participation into Sub-study IV will be only be offered to a subset of 20 transgender men/gender non-conforming individuals with vaginas enrolled at the UCSD AVRC. Transgender women enrolled at the UCSD AVRC who have undergone gender reassignment surgery with neovaginas will also be offered participation, although we expect this number to be guite low.

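### Sub-study IV, Aim 1: the stated 80% power needs about 40 participants per group, but about 20 in total are planned, which gives about 34% power when evenly split

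*Combined protocol and SAP*

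**What the plan says.** Section 9, Sub-study IV Statistical Considerations, Aim 1, plans a comparison of two independent groups on the week 24 TFV level in cervicovaginal fluid: "The primary analysis will compare those with any infection to those with no detected infection". The test is a t test or a Wilcoxon test, depending on the distribution.

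The sample size statement takes an "estimated mean concentration of 119 ng/mL and a standard deviation of 58 ng/mL in CVF TFV" from a steady-state PK study. It says "we have 80% power with a one-sided lower bound alpha of 0.05" to detect a difference between those with and without "STIs of 33 ng/mL or 28% reduction in CVF TFV levels in a sample of n=40". The 40 carries no label, and no infected share or dropout allowance is given.

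Section 10 sets the size of the sub-study: "Participation into Sub-study IV will be only be offered to a subset of 20 transgender men/gender non-conforming individuals with vaginas enrolled" at the UCSD centre. Transgender women at that centre who have neovaginas "will also be offered participation, although we expect this number to be" low.

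The Sub-study I sample size text in Section 9 adds context on the available pool: "Of our 300 person cohort, we estimate that 280 individuals will be MAAB". That leaves 300 − 280 = 20 others across all sites.

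**The concern.** The power statement and the enrolment statement do not fit together. If 40 is a total, it is twice the number to whom the sub-study is offered, before the expected few extra. If 40 is per group, it is four times that number.

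The consequence lies in how a null result is read. Section 7 counts two testable aims and one exploratory aim in Sub-study IV. Aim 1 is one of the testable ones, and Section 7 treats the genital TFV level as a surrogate for local drug efficacy. A reader who relies on 80% power for a 28% reduction could take a non-significant Aim 1 result as evidence that genital infections do not lower drug levels. At the planned size the data could not support that conclusion.

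**Working it through.** **Inputs, all from Section 9, Sub-study IV, Aim 1 unless noted.** SD 58 ng/mL; reference mean 119 ng/mL; difference 33 ng/mL (33/119 = 27.7%, stated as 28%); one-sided alpha 0.05; target power 80%; two independent groups. Planned number: 20 plus a few (Section 10). The infected share is not in the documents. An even split is assumed first because it favours the plan most, and other shares follow.

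**Reproducing the plan's figure.** By the normal approximation,

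n per group = 2 × [(1.645 + 0.842) × 58/33]² = 38.2, so 39 per group and 78 in total.

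The t test gives the same number: 80.1% power at 39 per group and 81.0% at 40 per group. The plan's 40 is therefore a per-group figure.

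**Power for 33 ng/mL at other sizes.** Two-sample t test, one-sided 0.05, noncentrality = 33 / [58 × √(1/n₁ + 1/n₂)], df = n₁ + n₂ − 2:

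| Reading | Split | Power |
|---|---|---|
| 40 per group | 40 v 40 | 81.0% |
| 40 in total, even | 20 v 20 | 54.9% |
| 40 in total, 40% infected (assumed) | 16 v 24 | 53.5% |
| 40 in total, 25% infected (assumed) | 10 v 30 | 45.4% |
| 40 in total, 10% infected (assumed) | 4 v 36 | 27.9% |
| 20 in total, even | 10 v 10 | 33.7% |
| 20 in total, 40% infected (assumed) | 8 v 12 | 32.8% |
| 20 in total, 25% infected (assumed) | 5 v 15 | 28.0% |
| 20 in total, 10% infected (assumed) | 2 v 18 | 18.1% |
| 20 plus 2 (assumed), even | 11 v 11 | 36.1% |
| 20 plus 6 (assumed), even | 13 v 13 | 40.7% |

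For example, at 10 v 10 the noncentrality is 33 / (58 × √0.2) = 33/25.94 = 1.27 on 18 df. The chance of missing a true 33 ng/mL difference is 1 − 0.337 = 66.3%.

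**Difference with 80% power, same test.**

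| Split | Difference | Share of 119 ng/mL |
|---|---|---|
| 40 v 40 | 32.5 ng/mL | 27.3% |
| 20 v 20 | 46.4 ng/mL | 39.0% |
| 13 v 13 | 58.2 ng/mL | 48.9% |
| 10 v 10 | 67.1 ng/mL | 56.4% |
| 5 v 15 | 77.4 ng/mL | 65.1% |

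At 10 v 10 the ratio to the stated difference is 67.1/33 = 2.03.

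**Other tests.** The Wilcoxon test that the plan allows has 30.1% power at 10 v 10 and 52.5% at 20 v 20 (8,000 simulations, normal data). A log scale, which the plan does not specify for TFV, has SD √ln(1 + (58/119)²) = 0.462 and difference −ln(1 − 33/119) = 0.325. It gives 44.8% at 10 v 10 and 70.5% at 20 v 20. A two-sided t test at 40 per group gives 71.0%.

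**Precision at the planned size.** The expected 95% half-width at 10 v 10 is 2.101 × 58 × √0.2 = 54.5 ng/mL.

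**The case against.** - **The 20 may be a local number.** The document describes one institution's part of a multi-site study, and the 20 are people enrolled at its own centre. A wider sub-study could lie behind the 40. But Section 10 restricts the offer to that subset, no other site is mentioned for Sub-study IV, and 40 in total would still give at most 55%.
- **The 280 of 300 estimate is weak support.** It is a Sub-study I planning figure for all sites and not a cap. Participants with neovaginas were assigned male at birth, so the remaining 20 do not bound the eligible pool. This objection stands. The estimate is context only, and the conclusion rests on the Aim 1 text and Section 10.
- **The infected share is unknown.** This is true, and any infection counts, including those found by the vaginitis, herpesvirus and HPV tests. The 34% already uses the most favourable split, and any other lowers it.
- **A one-sample test may have been meant.** With 20 people it would have 79.0% power. With 40 it would have 97.1%, so it does not explain the stated figure, and it is not the comparison that the plan describes.
- **It is one aim of a small sub-study.** This also stands. Neither the primary endpoint nor the main sample size is touched, which limits the priority. It does not make the stated power correct.

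**Conclusion.** The concern holds. Nothing in the documents labels the 40 or reconciles it with the 20, and the stated 80% is not delivered on either reading. Per group, it needs about 78 to 80 people against about 20 planned. As a total, it gives at most 55%. At the planned size the power for 33 ng/mL is about 34%, or 36% to 41% with an assumed two to six extra participants.

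These figures use the plan's own SD, difference and one-sided alpha. They assume an even split and a week 24 level from every participant. Dropout or an uneven split lowers them.

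**What to change.** Reconcile the Aim 1 sample size text in Section 9 with the Sub-study IV enrolment text in Section 10 on one number. State whether it is the total or the size of each group, give the assumed infected share, and restate the power or the detectable difference at that number. If 20 stands, wording such as this would do:

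*With 20 participants evenly split between infected and uninfected, a one-sided t test at 0.05 has about 34% power for a difference of 33 ng/mL; 80% power is reached only for a difference of about 67 ng/mL (56% of 119 ng/mL), and a larger one if the split is uneven.*

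If more participants or sites are intended, Section 10 should say so.

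It would also help to report Aim 1 as the estimated difference with its confidence interval, so that a null result is read with its uncertainty. That is good practice and not part of the correction itself.

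The cost is wording only, with no change to enrolment, visits or samples. The stated power becomes less favourable.

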10. HUMAN SUBJECTS

The study will enroll about 300 self-identified transgender or gender-nonconforming individuals ages 18 and older at all participating sites. UCSD and FHCSD plans to enroll up to 100 subjects.

Main Study Inclusion Criteria

- 1. Transgender identity, defined as identifying differently from sex assigned at birth.
- 2. Age 18 years or older.
- 3. Risk of acquisition of HIV as evident by one or more of the following:
 - I. Has at least one HIV infected sexual partner for ≥4 weeks.

OR

II. Anticipated or concern of unprotected anal or vagina sex with a partner in the next 3 months

OR

- III. Any partner in the past 12 months AND at least one of the following:
 - a. any condomless anal or vaginal sex in the past 12 months;
 - b. any STI diagnosed or reported in the past 12 months;
 - c. exchange of money, gifts, shelter, or drugs for sex;

OR

- IV. Post Exposure Prophylaxis (PEP) use in the past 12 months.
- 4. Negative for HIV infection by nucleic acid test (NAT) or other sensitive method such as 4th generation antibody- antigen test.
- 5. Acceptable renal function as measured by calculated creatinine clearance of at least 60 mL/min by the Cockcroft-Gault formula (eCcr (male) in mL/min = [(140 age in years) x (lean body weight in kg)] / (72 x serum creatinine in mg/dL) in the past 30 days.

Main Study Exclusion Criteria

- 1. Unable to give informed consent.
- 2. Active hepatitis B defined by a positive hepatitis B surface antigen (HBSAq)
- 3. Substantial medical condition, that in the opinion of the investigator would preclude participation, as defined by
 - gastrointestinal condition that would impair absorption of study drugs.
 - Known condition of reduce bone density (e.g. osteoporosis or osteogenesis imperfect) that significantly elevate the risk of bone fracture
 - Neurological or severe psychiatric condition that would significantly impair the ability to adhere to PrEP.
 - Tubular or glomerular kidney disease that could be exacerbated by tenofovir
 - Other medical condition that would unacceptably increase the risk of harm from study drug or significantly impair the ability to adhere to PrEP.
- 4. Suspected sensitivity or allergy to the study drug or any of its components.
- 5. Currently using an essential product or medication that interacts with the study drug such as the following:
 - Other antiretroviral agent (including nucleoside analogs, non-nucleoside reverse transcriptase inhibitors,

integrase inhibitors, protease inhibitors or investigational antiretroviral agents) – if currently on TDF/FTC for PEP or PrEP they can switch to study provided drug but can not continue any other antiretroviral agent.

- Agents with known nephrotoxic potential:
 - aminoglycoside antibiotics (including gentamicin)
 - IV amphotericin B
 - cidofovir
 - o cisplatin
 - foscarnet
 - IV pentamidine
 - IV vancomycin
 - o oral or IV gancyclovir
 - other agents with significant nephrotoxic potential
- Drugs that slow renal excretion
 - Probenecid
- Immune system modulators
 - Systemic chemotherapeutic agents (i.e. cancer treatment medications)
 - Ongoing systemic corticosteroids (with the exception of short courses of tapering steroid doses for asthma or other self- limited condition).
 - Interleukin-2 (IL-2)
 - Interferon (alpha, beta, or gamma)
- Other agent known to have a significant interaction with TDF or FTC
- 6. Proteinuria 2+ or greater by urine dipstick
- 7. Pregnancy (if individual has a uterus)
- 8. Other condition that in the opinion of the investigator would put the participant at risk or interfere with participation, complicate interpretation of study outcome data, or otherwise interfere with achieving the study objectives.

Participation into Sub-study IV will be only be offered to a subset of 20 transgender men/gender non-conforming individuals with vaginas enrolled at the UCSD AVRC. Transgender women enrolled at the UCSD AVRC who have undergone gender reassignment surgery with neovaginas will also be offered participation, although we expect this number to be guite low.

11. RECRUITMENT AND PROCEDURES PREPARATORY TO RESEARCH

Adaptive recruitment strategies will be employed as necessary. Our sites provide significant HIV testing for transgender individuals and the number of testers is enough to supply enrollment to this project. We will also use specific targeted recruitment and outreach to supplement the enrollment directly coming from the testing programs. Any recruitment materials will be submitted to the IRB for approval prior to use. One lesson learned from a previous PrEP study was that social network referral was a significant driver of enrollment. In our formative work through consultation with community advisory boards (CABs) and focus groups with members of the transgender community, it was evident that individuals within the transgender spectrum represent diverse and unique populations that are typically highly connected through interpersonal social networks. We will focus outreach efforts on social media sites, publications, and advocacy groups that specifically serve the transgender

community.

Additionally, UCSD and FHCSD are affiliated with numerous healthcare organizations throughout San Diego County that we will target for enrollment outreach, including the San Diego County Health and Human Services Agency (SDHHSA) and San Ysidro Health Center. The UCSD Early Test Program provides screening for acute HIV infection and reaches many at-risk individuals in San Diego (1-2% of tested are transgender) and can be used to access high-risk individuals. FHCSD is a community-based health organization that is the largest provider of services for minority, uninsured, indigent, and transgender populations in San Diego. FHCSD provides dedicated healthcare services to trans individuals, including PrEP, at their North Park "The Night Clinics" (TNC).

Recruitment materials/avenues will be developed by the AVRC Outreach Department, including sign-up sheets for participants to volunteer contact information at outreach events, recruitment business cards with study coordinator contact information, and classifieds advertising on websites and print media (e.g. newspapers, magazines). Any other recruitment materials e.g., flyers/posters, online recruitment materials, and e-mails to community doctors will be submitted to the IRB for review and approval prior to posting.

This study will utilize several social networking services to increase outreach and recruitment efforts, including *Grindr* and *Studykik* (www.studykik.com). The study will be promoted in *Grindr* in-app prompts and banners displaying IRB-approved language. All prompts and banners will link to a study-specific website that includes contact information for interested participants.

Studykik is a clinical research recruitment service connecting interested individuals to studies via social media communities. Studykik manages studies' social media presence on networking services including Instagram, Snapchat, Facebook, Twitter, Pinterest, and Google and other search engines. Our study will provide Studykik with basic inclusion/exclusion criteria, study site location, and IRB-approved recruitment language. Studykik will filter their database based on proximity to study site, study criteria, and target population; individuals identified in this manner will be provided the study's IRB-approved outreach material and, if interested in participating, will be connected to the study coordinators.

12. INFORMED CONSENT

This protocol and the informed consent document and any subsequent modifications will be reviewed and approved by the UCSD Institutional Review Board responsible for oversight of the study. Written informed consent will be obtained from the subject from a member of the study staff. At the time potential subjects contact us regarding the study, any questions they may have will be answered by a member of the study staff. If the potential subject is still interested in participating, a clinic visit will be scheduled. The subject will be informed of the time that needs to be allotted for their first visit in which the informed consent will be administered.

Individuals unable to speak English will not be excluded from participating in a study. The approved informed consent and any subsequent versions will be translated into Spanish and on a case by case situation any other language that is deemed necessary. The translated informed consents will be submitted to the IRB for approval. The consent process will include a qualified translator in the subject's native tongue. If a qualified UCSD translator is not available the Cyrom Language Line will be utilized as they have certified medical interpreters. The interpreter will sign and date at the end of the approved informed consent unless the Cyrom interpreter is utilized. In this situation, the study staff member involved in the consent process will document translator's name, ID#, and date of the translation at the end of the approved informed consent.

The informed consent will describe the purpose of the study, the procedures to be followed, and the risks, and benefits of participation. This information will be explained to the study subject in a face-to-face setting by the individual consent the subject. Subjects will be encouraged to ask questions throughout the consent process and encouraged to discuss their participation with trusted advisors, such as family members, close friends, etc. Subjects will be allotted sufficient time to consider whether or not to participate in the research study. After allowing the potential subject time to read the informed consent the study staff and/or investigator will answer and address any questions or concerns the subject may have. Once all questions and concerns have been addressed and the subject wishes to participate, they will be asked to sign the informed consent.

Also, during the consent process, the Health Insurance Portability and Accountability Act (HIPAA) Authorization

will be addressed. A copy of the consent and HIPAA Authorization form as well as the Notice of Privacy Practices booklet will be given to the subject.

